 Safety To assess the safety profile of each vaccine in all participants and by age group 	 Occurrence of any unsolicited systemic adverse events (AEs) reported in the 30 minutes after each vaccination Occurrence of solicited (pre-listed in the participant's diary card [DC]/electronic DC [eDC] and case report book [CRB]) injection site reactions and systemic reactions occurring up to 8 days after each vaccination Occurrence of unsolicited AEs up to 28 days after each vaccination Occurrence of medically attended adverse event (MAAEs) up to 28 days after each vaccination Occurrence of SAEs (including AESIs) throughout the study

*Depending on vaccination schedule/influenza previous vaccination: 1 dose received during the study = D29 and 2 doses received during the study = D57

Note: All AESIs will be collected in the PV database, regardless of the seriousness

Overall Design

Type of design	Parallel, multi-center
Phase	Phase III
Control method	Active-controlled Control Product = Fluarix® Quadrivalent (or other commercial names), Egg-based Influenza vaccine (split virion, inactivated) (IIV4) (GlaxoSmithKline Biologicals)

Study population	Healthy children aged 3 to 8 years
Countries	USA and Europe
Level and method of blinding	Modified double-blind (participant, Sponsor, and Investigator blinded)
Study intervention assignment method	Randomization

Brief Summary:

The purpose of this study is to demonstrate the non-inferior HAI immune response of RIV4 vs licensed IIV4 for the 4 strains based on the egg-derived antigen in all participants aged 3 to 8 years and to describe the immunogenicity and safety profile of RIV4 compared to IIV4 in participants aged 3 to 8 years.

Participants will be enrolled on the day of their first vaccination to receive 1 or 2 doses 28 days apart of either RIV4 or IIV4; depending on if they were previously vaccinated against influenza or previously unvaccinated against influenza, respectively; and will be followed for 6 months after the last vaccination.

Number of Participants:

Approximately 1412 participants 3 to 8 years of age (approximately 50% participants in the age group 3-5 years and 50% participants in the age group 6-8 years) is expected to be randomized. Approximately 50% of participants randomized will be previously unvaccinated against influenza and 50% of participants will be previously vaccinated against influenza.

Intervention Groups and Duration:

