Eligible participants 3-8 years of age will receive intramuscular (IM) injection(s) of either RIV4 or IIV4 at D01.

Participants will receive either 1 or 2 doses 28 days apart of either RIV4 or IIV4 depending on whether they were previously vaccinated against influenza or previously unvaccinated against influenza, respectively.

In order to maintain consistent vaccination schedule rules across all countries and sites for the classification of children considered previously influenza vaccinated and previously influenza unvaccinated, all study sites will follow the US Advisory Committee on Immunization Practices recommendations for influenza vaccine (1).

• Previously unvaccinated participants are defined as participants who have not received at least 2 doses of seasonal influenza vaccine in prior influenza seasons. These participants will receive 2 doses of the study vaccine 28 days apart after enrolling in the study. Participants who have received only one dose of any influenza vaccine in the past or participants whose vaccination history is unknown will also be considered as previously unvaccinated participants when enrolling and receive 2 doses of the study vaccine 28 days apart.

• Previously vaccinated participants are defined as participants who have received at least 2 doses of seasonal influenza vaccine in prior influenza seasons. These participants will receive only 1 dose of the study vaccine after enrolling in the study.

	RI	V4			II	V4		Total
	(N=	706)			(N=	706)		(N=14 12)
against i	vaccinated nfluenza ose	unvaccina influ	ously ted against enza days apart	against i	vaccinated nfluenza ose	unvaccina influ	ously ted against enza days apart	
Approxim ately 50% aged 3 to 5 years	Approxim ately 50% aged 6 to 8 years	Approxim ately 50% aged 3 to 5 years	Approxim ately 50% aged 6 to 8 years	Approxim ately 50% aged 3 to 5 years	Approxim ately 50% aged 6 to 8 years	Approxim ately 50% aged 3 to 5 years	Approxim ately 50% aged 6 to 8 years	
3:	53	35	53	3:	53	3:	53	1412

The participation duration will be approximately 6 months for participants previously vaccinated against influenza and approximately 7 months for participants previously unvaccinated against influenza.

Study interventions

Investigational medicinal product 1: Quadrivalent Recombinant influenza vaccine (RIV4) <year season> NH

- Form: solution for injection

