An unsolicited AE is an observed AE that does not fulfill the conditions of solicited reactions, ie, pre-listed in the CRF in terms of diagnosis and onset window post-vaccination. For example, varicella or a solicited term such as headache starting after the solicited observation period (eg, headache starting on Day 10 post-vaccination in the case where headache occurring between the day of vaccination and the next 7 days is pre-listed in the protocol and CRF as a solicited reaction).

An unsolicited AR is an unsolicited AE that is considered related to an IMP.

Unsolicited AEs includes both serious (SAEs) and non-serious unsolicited AEs.

All unsolicited AEs occurring at and around the IMP injection/administration site are to be considered by default as related to the IMP administered at that site and are therefore referred as unsolicited injection/administration site ARs.

All unsolicited AEs which are not at and around the IMP injection/administration site, are referred as systemic unsolicited AE. For each unsolicited systemic AE, the investigator assesses the relationship to the IMP. Systemic AEs assessed as related to IMP are referred as systemic ARs.

Adverse Event of Special Interest (AESI):

An adverse event of special interest (serious or non-serious) is one of scientific and medical concern specific to the Sponsor's study intervention or program, for which ongoing monitoring and rapid communication by the investigator to the Sponsor can be appropriate. Such an event might warrant further investigation in order to characterize and understand it. Depending on the nature of the event, rapid communication by the study Sponsor to other parties (eg, regulators) might also be warranted.

Medically Attended AE (MAAE)

An MAAE is a new onset or a worsening of a condition that prompts the participant or participant's parent/legally acceptable representative to seek unplanned medical advice at a physician's office or Emergency Department. Physician contact made over the phone or by e-mail will be considered a physician office visit for the purpose of MAAE collection. This includes medical advice seeking during the study visit or routine medical care. This definition excludes pediatric check-ups, follow-up visits of chronic conditions with an onset prior to entry in the study, and solicited reactions.

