3.3 Populations for Analyses

For the purposes of analysis, the following analysis sets will be defined:

Participant Analysis Set	Description
Randomized	All participants randomized by study IRT to one of the study groups.
Safety Analysis Set (SafAS)	Participants who have received at least one dose of the study vaccine. All participants will have their safety analyzed after each dose according to the vaccine they actually received, and after any dose according to the vaccine received at the 1st dose.
	Safety data recorded for a vaccine received out of the protocol design will be excluded from the analysis (and listed separately).
Full analysis set (FAS)	Subset of randomized participants who received at least 1 dose of the study vaccine and had a post-vaccination blood sample. For the assessment of the immune response by SN assay, the analysis will be performed on the participants from FAS who were randomized in the exploratory subset (FAS-SN).
	Participants will be analyzed according to the intervention to which they were randomized.
Per-protocol analysis set (PPAS)	Subset of the FAS. Participants presenting with at least one of the following criteria will be excluded from the PPAS:
	Participant did not meet all protocol-specified inclusion criteria or met at least one of the protocol-specified exclusion criteria
	Participant did not complete the vaccination schedule
	Participant received a vaccine other than the one that he / she was randomized to receive
	Preparation and / or administration of vaccine was not done as per-protocol
	Participant did not receive vaccine in the proper time window
	Participant did not provide the post-dose serology sample at visit 2 or at visit 3 in the proper time window ([D26, D39] or VAC2+[D26, D39] respectively) or a post-dose serology sample was not drawn at visit 2 or visit 3
	Participant received protocol-prohibited medications impacting or that may have an impact on the immune response, as specified in the database following data review of concomitant medications.
	Any other deviation identified during the study conduct and identified as relevant by the clinical team during data review, ie, indicated as excluding participants from this analysis set in the manual deviations dataset.

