For solicited reactions, the denominator will be the total number of participants who have nonmissing data for the endpoint considered.

For unsolicited AEs, the denominator will be the total number of participants who were vaccinated.

In terms of contents, solicited reactions will be presented by time to onset, maximum severity, number of days of occurrence and action taken; unsolicited AEs will be presented by causal relationship, time of onset, maximum severity and duration; SAEs will be presented by causal relationship, seriousness and outcome.

Subgroup analyses will also be performed; in particular, the main safety endpoints will be described according to age subgroups (3 to 5 and 6 to 8 years), previous vaccination status, sex and race, as appropriate according to number of participants in the respective subgroups.

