4.2.1.2.3 Last Vaccination

Last vaccination before an unsolicited AE will be derived from the pre-visit numbers provided in the clinical database and will be calculated as follows:

- If an unsolicited AE has a non-missing pre-visit number, the pre-visit number will be used to determine the last vaccination before the unsolicited AE
- If the pre-visit number is missing and the start date is complete (ie, including day), then the start date will be used to determine the last vaccination before the unsolicited AE
- If an unsolicited AE has a missing pre-visit number and a partial start date (at least day missing), the unsolicited AE will be considered as post injection 1.

Confidential/Proprietary Information Page 32 of 40

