4.2.1.2.7 Serious Adverse Events

An event will be considered as a serious event if "Yes" is checked for "Serious" in the CRF.

SAEs will be analyzed within 28 days after each vaccination, from D29 to 180 days after each vaccination, and within 180 days after each vaccination.

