4.2.1.2.8 Adverse Events of Special Interest

An event will be considered as an AESI if "Yes' is checked for "Is the event an AESI?" in the CRF.

AESIs will be analyzed within 28 days after each vaccination, from D29 to 180 days after each vaccination, and within 180 days after each vaccination.

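### In two-dose children, dose 2 at about D29 cuts off the 180-day SAE and AESI windows after dose 1, so the dose-1 long-window percentages are diluted or near-empty by construction

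*SAP*

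**What the plan says.** **Windows.** SAP 4.2.1.2.7 analyses SAEs within 28 days after each vaccination, then "from D29 to 180 days after each vaccination, and within 180 days after each vaccination". SAP 4.2.1.2.8 starts the same way ("AESIs will be analyzed within 28 days after each vaccination") and adds the same two long windows. Neither section says what happens to the long windows after dose 1 in a child who goes on to receive dose 2.

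**Attribution.** Under SAP 4.2.1.2.3, when a pre-visit number is recorded, "the pre-visit number will be used to determine the last vaccination before the unsolicited AE". If it is missing, a complete start date is used. If the start date is also partial, the event goes to injection 1. The rule covers SAEs, because Protocol 10.2.1 states: "Unsolicited AEs includes both serious (SAEs) and non-serious unsolicited AEs".

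**Denominator.** SAP 3.4.3: "For unsolicited AEs, the denominator will be the total number of participants who were vaccinated". It is not restricted to children still at risk in the window.

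**Schedule.** Protocol 1.1: "Approximately 50% of participants randomized will be previously unvaccinated against influenza", and "These participants will receive 2 doses of the study vaccine 28 days apart after enrolling in the study". Protocol Table 1.2 allows the second vaccination visit from 2 days early to 7 days late.

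**Other planned presentations.** The safety analysis set (SAP 3.3) is analysed after each dose and also "after any dose according to the vaccine received at the 1st dose". The Protocol 1.1 synopsis plans safety by age stratum and number of doses. SAP 3.4.3 adds main safety endpoints by previous vaccination status, where numbers allow.

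**The concern.** Each rule is reasonable alone, but together they do not fit. The window promises 180 days after dose 1, the attribution rule ends a two-dose child's dose-1 period at about D29, and the denominator still counts that child in full. A reader of a post-dose-1 table would take the denominator as children followed for 180 days after that dose, when half of them can hardly contribute an event to the later part.

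The safety objective is to describe the profile of each vaccine, so the absolute percentages of serious and special-interest events in children are themselves the result. Percentages set partly by how the window is built do not describe either vaccine.

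**Working it through.** **Inputs**
- Planned children per arm: 353 one-dose and 353 two-dose, 706 in all (Protocol 1.1 and Table 6.2).
- Dose 2 at V01 + 28 days, window -2 to +7, so D27 to D36 (Protocol Table 1.2).
- Follow-up to V01 + 180 days for one dose and V02 + 180 days for two doses (Protocol Tables 1.1 and 1.2).

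**The plan's own figures reproduce.** 1200/0.85 = 1412 enrolled, and 4 x 353 = 1412. D01 + 180 days = D181, and D29 + 180 days = D209. Both match the schedules. The SAP gives no figure for the long windows themselves.

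**Step 1: late-window days open to a two-dose child after dose 1.** Days 29 to 180 after dose 1 are 180 - 29 + 1 = 152 days. With dose 2 on D27 or D29, none of them precedes dose 2. With dose 2 on D36, 6 or 7 do, depending on whether the window starts on D30 or D29. SAP 4.2.1.2.4 runs the 28-day window through D29, so that boundary is unclear; starting on D29 makes the window 153 days and hardly changes the results. The two-dose child's share is thus 0 to 7/152 = 0 to about 5%.

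**Step 2: late-window coverage after dose 1, both schedules pooled.**

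Share = (353 x 152 + 353 x x) / (706 x 152)
- x = 0: 0.500
- x = 7: 0.523

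**Step 3: 180-day coverage after dose 1, both schedules pooled.**

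Share = (353 x 180 + 353 x y) / (706 x 180), where y is the number of days from dose 1 to dose 2
- y = 26 (D27): 0.572
- y = 28 (D29): 0.578
- y = 35 (D36): 0.597

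**Step 4: effect on percentages.** Assume a constant event rate and complete follow-up. The pooled post-dose-1 percentage is then understated by 1 - 0.523 to 1 - 0.500, about 48-50%, in the late window. Over 180 days it is understated by 1 - 0.597 to 1 - 0.572, about 40-43%.

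**Illustration.** The documents give no SAE or AESI rate. For assumed late-window risks of 0.5%, 1% and 2%, the pooled table would show about 0.25-0.26%, 0.50-0.52% and 1.00-1.05%.

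**Step 5: if the table is split by number of doses.** The one-dose column is fully observed and correct. The two-dose late-window column after dose 1 is 0 to about 5% filled, so it shows close to zero over about 353 children per arm.

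**The case against.** The strongest reply is that nothing the trial must report is damaged. The endpoint is SAEs and AESIs throughout the study, and the analysis after any dose serves it. SAEs are collected until 6 months after the last vaccination (Protocol 8.3.1), so none is lost: a two-dose child's later events appear under dose 2 and under any dose. Randomisation is 1:1 and stratified by vaccination status, so neither vaccine is favoured. Safety is descriptive. The interim analysis uses summaries up to D29 after the last vaccination, plus listings that run beyond it. All of this stands.

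It is also fair that the halving depends on a pooled table that the documents do not show, and that the protocol plans analysis by number of doses. That limits the claim but does not remove it: splitting replaces a diluted percentage with a near-empty cell that looks like 180 days of reassuring data.

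A reader might infer two stronger things.
- **Double counting under both doses.** If calendar windows were applied without the attribution rule, 145 to 154 of the 180 days after dose 2 (81-86%) would also lie in the dose-1 window. But SAP 4.2.1.2.3 assigns each event once. Its exception, a missing pre-visit number with a partial date, sends the event to injection 1, still once.
- **A false rise from dose 1 to dose 2.** The arithmetic would allow it, but neither document plans a comparison of late-window events between doses.

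**Conclusion.** The point holds as a minor but real error in descriptive safety tables. It is more than missing detail: the stated windows, attribution rule and denominator together yield a dose-1 long-window percentage that is either diluted or nearly empty.

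In a table pooling both schedules, coverage is about 50-52% of the nominal late-window person-time and 57-60% of the 180-day person-time. The understatement of 48-50% and 40-43% rests on four assumptions: a constant event rate, complete follow-up, the planned 353/353 split, and every two-dose child receiving dose 2 on time. A child who stops after dose 1 because of a definitive contraindication but stays in safety follow-up (Protocol 7.1.2) legitimately contributes to the late window after dose 1, so coverage would be slightly higher.

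The tables after any dose, the study-wide endpoint and the balance between arms are unaffected.

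**What to change.** In SAP 4.2.1.2.7 and 4.2.1.2.8:
1. Keep the 28-day window after each vaccination. Define the two long windows from the last vaccination received: *after 28 days up to 180 days after the last vaccination* and *within 180 days after the last vaccination*. Starting the late window after 28 days also settles the D29 boundary.
2. Present both long windows by number of doses actually received. A child who never receives dose 2 is then handled correctly, because dose 1 is the last dose.
3. For dose 1 of two-dose children, report only the period from dose 1 to dose 2, and say so in the table footnote.
4. Cross-refer to the attribution rule in 4.2.1.2.3, so that calendar windows are not programmed by mistake.

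This matches the follow-up already planned, which runs 180 days from the last dose (D181 or D209). The cost is SAP wording and table shells only, with no new data.

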4.2.1.2.8 Adverse Events of Special Interest

An event will be considered as an AESI if "Yes' is checked for "Is the event an AESI?" in the CRF.

AESIs will be analyzed within 28 days after each vaccination, from D29 to 180 days after each vaccination, and within 180 days after each vaccination.

4.2.2 Other Safety Endpoints

4.2.2.1 Pregnancy

Not applicable.

4.2.2.2 Action Taken

This information will be summarized as collected, including missing observations. No derivation or imputation will be done.

4.2.2.3 Seriousness

This information will be summarized as collected. No derivation or imputation will be done.

4.2.2.4 Outcome

This information will be summarized as collected. No derivation or imputation will be done.

4.2.2.5 Causal Relationship

This information will be summarized as collected in the field "Relationship to study vaccine". Missing causal relationship will be handled as described in Section 3.4.4.1.2. Relationship to study procedure is only presented in the listing.

Confidential/Proprietary Information Page 34 of 40

VV-CLIN-0628295 5.0

4.2.2.6 Adverse Events Leading to Study Discontinuation

This information will be summarized as collected. A flag is available in the clinical database for all AEs to identify AEs leading to discontinuation before the end of active phase.

In general, the items that are counted are:

- Disposition table: A participant who, on the "Completion at End of Active Phase" form question "What was the participant's status?" has "Adverse Event" checked.
- Safety overview table: A participant who has either on the "Completion at End of Active Phase" form, question" What was the participant's status?" has "Adverse Event" checked or lists a solicited AE that has "Caused Study Termination" checked that is at least Grade 1 or an unsolicited AE that has "Caused Study Discontinuation" checked that is at least Grade 1 or missing and is within the time period indicated.
- System Organ Class (SOC)/Preferred Term (PT) table: A solicited AE that has "Caused Study Termination" checked that is at least Grade 1 or an unsolicited AE that has "Caused Study Discontinuation" checked that is at least Grade 1 or missing and is within the time period indicated.

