1.3 Schedule of Activities (SoA)

Visit procedures are detailed in the Operating Guidelines.

Table 1.1: Schedule of activities for previously vaccinated participants 3-8 years of age

Phase III Study. 2 Visits. 1 Vaccination. 2 Blood Samples. 6 Months' Duration Per Particinant

Visit/Contact	Collection of information in the CRF	Visit 1	Phone Call 1*	Visit 2	Phone Call 2 6-month follow-up†
Study timelines (Days)		D01	D09	D29	D181
Time interval (Days)		NA	V01+8D	V01 + 28D	V01 + 180D
Time windows (Days)		NA	[+2 D]	[-2, +7 D]	[+14 D]
Visit procedures:					
Informed consent	Х	Х			
Inclusion/exclusion criteria	Х	Х			
Collection of demographic data§§	Х	Х			
Collection of medical history*** (Significant medical history)	Х	Х			
Collection of concomitant medications	X Reportable concomitant medications	28 da	28 days after vaccination	nation	
History of Influenza vaccination	Х	Х			
Physical examination §		Х		Х	
Pre-vaccination temperature		Х			
	•				

Confidential/Proprietary Information Page 16 of 86

Sanofi Pasteur 529 – Quadrivalent Recombinant Influenza Vaccine

VAP00026 Protocol Version 3.0

Visit/Contact	Collection of information in the CRF	Visit 1	Phone Call 1*	Visit 2	Phone Call 2 6-month follow-up†
Study timelines (Days)		D01	D09	D29	D181
Time interval (Days)		NA	V01+8D	V01 + 28D	V01 + 180D
Time windows (Days)		NA	[+2 D]	[-2, +7 D]	[+14 D]
Visit procedures:					
Randomization Contact Interactive Response Technology (IRT) system for randomization, participant number, dose number and SN subset	Х	Х			
Blood sampling (BL) (5 mL)	Х	BL0001**		BL0002	
Vaccination (vac)	X	Х			
Immediate surveillance (30 min)	Х	Х			
Diary card (DC) / electronic DC [eDC] / Memory Aid (MA) provided		DC/eDC		MA	
DC/eDC Reviewed and collected				DC/eDC††	
MA Reviewed					MA
Collection of solicited injection site and systemic reactions	Х	7 day vaccii	7 days after vaccination		
Collection of unsolicited adverse events (AEs)	Х	28 day	28 days after vaccination	ination	
Collection of medically attended AEs (MAAEs)	Х	28 day	28 days after vaccination	ination	
Collection of information on SAEs, including AESIs	Х	To be re	sported at an	To be reported at any time during the study	ng the study
End of Active Phase participation record	Х			Х	
Six months follow-up participant record	Х				X

Confidential/Proprietary Information Page 17 of 86

Sanofi Pasteur 529 – Quadrivalent Recombinant Influenza Vaccine

VAP00026 Protocol Version 3.0

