7.2 Participant Discontinuation/Withdrawal from the Study

- A participant may be withdrawn from the study at any time at his/her parent(s)/legally acceptable representative own request or may be withdrawn at any time at the discretion of the investigator for safety, behavioral, or compliance reasons. This is expected to be uncommon.
- The reason for withdrawal should be clearly documented in the source documents and in the CRF: Adverse Event, Lost to Follow-up, Protocol Deviation, or Withdrawal by Parent / Legally Acceptable Representative.

- The participant will be permanently discontinued both from the study intervention and from the study at that time.
- If the participant's parent(s)/legally acceptable representative withdraw(s) consent for disclosure of future information, the Sponsor may retain and continue to use any data collected before such a withdrawal of consent.
- If a participant's parent(s)/legally acceptable representative withdraw(s) consent, they may request destruction of any biological samples taken (unless local law requires not to destroy them), and the investigator must document this in the site study records.
- Withdrawn participants will not be replaced.

Follow-up of Discontinuations

For participants who have prematurely terminated the study, the site should attempt to contact them and complete all scheduled safety follow-ups, except if they specified that they do not want to be contacted again and it is documented in the source document.

For participants where the reason for early termination is lost to follow-up, the site will not attempt to obtain further safety information. See Section 7.3 for definition of "lost to follow-up".

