4.2.1.1.2 Maximum Intensity

Maximum overall intensity is derived from the daily intensities computed as described in Section 4.2.1.1 and is calculated as the maximum of the daily intensities over the period considered.

4.2.1.1.3 **Presence**

Presence is derived from the maximum overall intensity over the time period considered:

- None: No presence
- Grade 1, Grade 2, or Grade 3: Presence
- Missing or Unknown: Missing presence

Participants with at least one non-missing presence for a specific endpoint will be included in the analysis. Conversely, those without a non-missing presence will not be included in the analysis of the endpoint.

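### A solicited reaction flagged as causing withdrawal but left ungraded is always lost from the SOC/PT discontinuation table, and sometimes from the safety overview

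*SAP*

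**What the plan says.** SAP 4.2.2.6 defines three tables for adverse events leading to study discontinuation.

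- **Disposition table.** This uses the completion form alone: "Disposition table: A participant who, on the 'Completion at End of Active Phase' form question 'What was the participant's status?' has 'Adverse Event' checked". There is no grade condition.
- **Safety overview table.** This has alternative routes. One is the form: "Safety overview table: A participant who has either on the 'Completion at End of Active Phase' form", with the same Adverse Event status. Another is the event record: "or lists a solicited AE that has 'Caused Study Termination' checked that is at least Grade 1". The third is a flagged unsolicited event "that is at least Grade 1 or missing and is within the time period indicated".
- **SOC/PT table.** This has the two event routes only, with the same grade conditions; the solicited route is again "a solicited AE that has 'Caused Study Termination' checked that is at least Grade 1". The form plays no part.

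The grade of a solicited reaction is derived under SAP 4.2.1.1. Daily intensity may be classed as Missing (Unknown), the maximum is taken over the daily intensities, and 4.2.1.1.3 then states "Missing or Unknown: Missing presence". By contrast, SAP 4.2.1.2.1 accepts an unsolicited event once it has a verbatim term and is not Grade 0.

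Protocol 7.2 lists the withdrawal reasons as "Adverse Event, Lost to Follow-up, Protocol Deviation, or Withdrawal by Parent / Legally Acceptable Representative".

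**The concern.** The two kinds of event carry the same type of flag: the site has recorded that the event ended the child's participation. For unsolicited events the flag counts even without a grade. For solicited reactions it does not, and 4.2.2.6 gives no reason for the difference, although it opens by saying that the information will be summarised as collected.

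Solicited reactions are related to the vaccine by convention (SAP 3.4.5.1.2), so any event removed is a vaccine-related withdrawal. The rule also departs from how the SAP treats other gaps in unsolicited AE data: a missing causal relationship is taken as related (3.4.5.1.2), and a missing time of onset stays in the 28-day tables (4.2.1.2.4).

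What is at stake is the accuracy of a descriptive tolerability count and the agreement between two tables that a reader will compare. No primary or secondary immunogenicity result depends on it.

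**Working it through.** There is no figure in the plan to reproduce. The check applies the counting rules to each possible case.

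**Step 1: can a flagged solicited reaction end up without a grade?** The rules in SAP 4.2.1.1 close most routes:

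- If CRF presence is No and all days are missing, every day becomes None (except for fever).
- A reaction too large to measure becomes Grade 3.
- The maximum is taken over the daily intensities. I read this as meaning that one graded day is enough.

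No rule covers a reaction that the site reports as present with every daily record missing. Its maximum intensity, and so its presence, is missing. SAP 3.4.5.1.3 sends missing solicited intensities back to 4.2.1.1, which does not fill the gap. The case is therefore possible, but narrow.

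**Step 2: apply SAP 4.2.2.6 to events with a missing grade.** The unsolicited events are taken to fall within the time period indicated.

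| Flagged event, grade missing | Form status | Disposition | Safety overview | SOC/PT |
|---|---|---|---|---|
| Solicited | Adverse Event | counted | counted (form route) | **not counted** |
| Solicited | another reason | not counted | **not counted** | **not counted** |
| Unsolicited | Adverse Event | counted | counted | counted |
| Unsolicited | another reason | not counted | counted | counted |

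**Step 3: isolate the effect of the grade rule.** Compare solicited with unsolicited at the same form status.

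- Disposition: identical in both pairs, so the grade rule never changes it.
- Safety overview: differs only when the form gives a status other than Adverse Event.
- SOC/PT: differs in both pairs, so the event is always lost.

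In the first row the child is in the overview, but no SOC/PT term accounts for the withdrawal. Every difference is an omission, so the filter can only lower a count.

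**Step 4: size.** One child is 1/706 = 0.14% of a planned arm. The documents give no expected number of AE-related withdrawals or of ungraded flagged reactions. Purely as illustration, if an arm had 1 to 5 such withdrawals (an assumption), omitting one would remove 1/1 = 100% to 1/5 = 20% of the count. That range does not say whether any case will occur.

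**The case against.** The strongest defence is that the asymmetry follows from the SAP's own definitions. Solicited presence is derived from intensity, so an ungraded reaction has missing presence; an unsolicited event needs no grade to exist. This explains the wording. It does not justify discarding an event that the site has recorded as the cause of withdrawal. If the Grade 1 condition is there to exclude reactions derived as None, adding 'or missing' still excludes them.

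The second defence is that grades will rarely be missing, and most of this stands. A reader might infer that ungraded reactions cluster in early withdrawals, because the schedule for previously vaccinated children puts "DC/eDC Reviewed and collected" at Visit 2, which such a child may not attend. The documents do not establish this:

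- Protocol 7.2 asks sites to try to contact early terminators and complete the safety follow-up, unless contact is refused or the child is lost to follow-up.
- Protocol 8.3.2 has staff interview parents and capture in source what the diary lacks.
- Protocol 8.3.3 requires events that led to discontinuation to be followed.
- Protocol 10.2.5 calls for an intensity grade for each AE.

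These steps reduce the gap without closing it.

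Third, the three tables use different sources by design, so some disagreement between them is expected whatever the grade rule. That is correct. What this rule adds is the mismatch between overview and SOC/PT in the first row of the table.

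**Conclusion.** The point holds as a minor one. A flagged solicited reaction with no usable intensity on any day is always omitted from the SOC/PT table, and is omitted from the safety overview only when the completion-form status is not Adverse Event. The effect is descriptive and in one direction, and its frequency cannot be computed from the documents. It rests on two readings of the SAP: that one graded day gives a maximum intensity, and that a reaction reported as present with all days missing stays missing.

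Two stronger readings are not supported.

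- A reader might infer that such children vanish from the discontinuation tables altogether. A child whose form status is Adverse Event stays in disposition and overview. Absence from all three tables also needs a form reason that does not match the checked flag, and the absence from disposition then comes from the form entry, not from the grade rule.
- A reader might infer that the firewall committee's review is affected. SAP 3.5.1 gives that committee a listing of AEs leading to discontinuation, and 3.5.2.4 says it includes all data in the database. The grade conditions in 4.2.2.6 are written for named tables, and no text applies them to the listing.

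**What to change.** In the safety overview and SOC/PT bullets of SAP 4.2.2.6, change the solicited condition to at least Grade 1 or missing, and show such events with intensity Missing. Leave the presence derivation in 4.2.1.1 unchanged, so that the reactogenicity percentages do not move. Make the change before the final database lock; Protocol 9.4 provides for the SAP to be amended before any lock.

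The cost is one phrase in two bullets and a matching programming change, with no new data collection. There are two downsides: reported AE-related discontinuations may rise slightly, and a few events may be tabulated here whose presence is classed as missing in the reactogenicity tables. A footnote can explain the latter.
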